3.4.2.2 Pause Rules

Study pause rules will be continuously monitored during all phases of the study by the investigators, study medical monitor, Sponsor medical lead, IST, and SMC (as warranted). If the investigator, study medical monitor, Sponsor medical lead, IST, or SMC request that the study be paused due to a safety concern, further study vaccine administration in the affected cohort and at higher dose levels will be suspended, but all other planned procedures relating to safety, reactogenicity, and immunogenicity assessments will continue as described in the protocol.

The occurrence of any of the events listed in Table 2, regardless of dosing group, will result in immediate suspension of dosing and enrollment in the cohort. An unscheduled meeting of the SMC will be convened to assess specific data concerns and to make recommendations.

The Sponsor will notify the Center for Biologics Evaluation and Research within 48 hours in the event of a study pause.

Table 2: Pause Rules Based on the Occurrence of a Single Adverse Event and Adjudicated by the SMC

Pause Rule	Adverse Event	Number of Participants per Dose Cohort
1	Any serious adverse event that cannot be reasonably attributed to a cause other than vaccination	≥ 1
2	Any Grade 4 adverse event that cannot be reasonably attributed to a cause other than vaccination	≥ 1
3	Any systemic immediate hypersensitivity reaction within 60 minutes after the study vaccination	≥ 1

Abbreviation: SMC = Safety Monitoring Committee.

Table 3 summarizes safety events that will pause study dosing based on defined threshold levels, which are aggregate incidences relative to the number of exposed participants within a dosing group. An unblinded statistician may be consulted to determine if a pause rule has been met.

Table 3: Pause Rules Based on the Occurrence of Adverse Events in a Proportion of Participants

Pause Rule	Adverse Event	Number of Participants per Dose Cohort ^a	
4	Any Grade 3 solicited local adverse event lasting more than 24 hours in an mRNA-1893 cohort ^b within the 7-day (Days 1-8) post-vaccination period	≥ 20% and ≥ 2 participants/group	
5	Any Grade 3 solicited general adverse event lasting more than 24 hours in an mRNA-1893 cohort ^b that cannot be reasonably attributed to a cause other than vaccination, within the 7-day (Days 1-8) post-vaccination period	\geq 20% and \geq 2 participants/group	

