6	Any ≥ Grade 3 unsolicited adverse event in an mRNA-1893 cohort ^b that cannot be reasonably attributed to a cause other than vaccination OR Any ≥ Grade 3 laboratory abnormality ^c in an mRNA-1893 cohort ^b that cannot reasonably be attributed to a cause other than vaccination	≥ 20% and ≥ 2 participants/group	

^a For the first 5 participants in each dose level cohort, the pause rule will be considered met if 2 of the first 5 participants experience the same event regardless of dosing group.

If a pause is triggered in the study, each participant's clinic visits will continue until the next scheduled vaccination visit. If a pause affects a participant's vaccination visit, the window for that participant's vaccination visit will be suspended until the pause is lifted and vaccination can resume. Once the pause is lifted at a site, vaccination should be reinstated as soon as possible. Clinic visits should thereafter (Day 36 [+3 days], Day 57 [-7/+14 days], Month 7 [± 14 days], and Month 13 [± 14 days]) be scheduled as if participants had received their second vaccination within the 28 (+14) day window. The Dose 2 window may be extended to 28 (+14) days at the discretion of the principal investigator and with approval of the study medical monitor on a case by case basis for participants whose window is affected by a study pause.

b The rate of adverse events and laboratory abnormalities will be computed based on the number of exposed participants who have provided safety data (i.e., have completed a post-dosing visit for assessment of safety).

Grading of laboratory parameters will be based on the US Food and Drug Administration Guidance for Industry "Toxicity grading scale for healthy adult and adolescent volunteers enrolled in preventive vaccine clinical trials" (DHHS 2007).

If a pause is prolonged such that the second vaccination takes place outside the 28 (+14) day window, the Sponsor has the option to add additional participants in a dosing cohort to achieve the original number of participants planned for dosing within the 28 (+14) day window. If a participant is in the Screening Phase for more than 28 days as the result of a pause, the participant may be rescreened for study eligibility (and will receive a new screening number) as long as the participant continues to provide consent to participate in the study.

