3.5.1 Safety Telephone Calls

A safety telephone call is a telephone call made to the participant by trained site personnel. This call will follow a script, which will facilitate the collection of relevant safety information. The participant will be interviewed according to the script, about occurrence of AEs, MAAEs, SAEs, AESI, or AEs leading to study withdrawal and concomitant medications associated with those events will be collected.

Additionally, in the Vaccination Phase of the study, the site will telephone the participant for safety monitoring on each of the 2 days after study vaccination (i.e., Day 2 and Day 3 after the first vaccination and Day 30 and Day 31 after the second vaccination). The purpose of this safety telephone call is to identify any rash or Grade 3 local and systemic reactogenicity AEs (solicited AEs) that may occur within 48 hours after study vaccination and to ensure that they are recorded in the eCRF and reported to the medical monitor in a timely manner.

The timing of the safety telephone calls is provided in Table 5.

All safety information described by the participant must be documented in source documents and not documented on the script used for the safety telephone contact.

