3.5.7.1.1 Definitions

An AE is defined as any untoward medical occurrence associated with the use of a drug in humans, whether or not considered drug related. Participants will be instructed to record any AEs (solicited or unsolicited) in the diary card.

A treatment-emergent AE (TEAE) is defined as any event not present before exposure to vaccine or any event already present that worsens in intensity or frequency after exposure.

A suspected adverse reaction is any AE for which there is a reasonable possibility that the vaccine caused the AE. For the purposes of investigational new drug safety reporting, "reasonable possibility" means that there is evidence to suggest a causal relationship between the vaccine and the AE. A suspected adverse reaction implies a lesser degree of certainty about causality than adverse reaction, which means any AE caused by a vaccine. Adverse reactions are a subset of all suspected adverse reactions for which there are reasons to conclude that the drug caused the event.

An unsolicited AE is any AE reported by the participant that is either (1) not specified as a solicited AE in the protocol or (2) specified as a solicited AE in the protocol, but its onset occurs outside of the protocol-defined post-vaccination period for reporting solicited AEs (i.e., for the 7 days after each vaccination; Section 3.5.6 for additional information on solicited safety measures).

An AE or suspected adverse reaction is considered "unexpected" if it is not listed in the IB or is not listed at the specificity or severity that has been observed with the vaccine being tested or, if an IB is not required or available, it is not consistent with the risk information described in the general investigational plan or elsewhere in the current application. For example, under this definition, hepatic necrosis would be unexpected (by virtue of greater severity) if the IB referred only to elevated hepatic enzymes or hepatitis. Similarly, cerebral thromboembolism and cerebral vasculitis would be unexpected (by virtue of greater specificity) if the IB listed only cerebral vascular accidents. "Unexpected," as used in this definition, also refers to AEs or suspected adverse reactions that are mentioned in the IB as occurring with a class of drugs or as anticipated from the pharmacological properties of the drug but are not specifically mentioned as occurring with the particular drug under investigation.

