3.6 Statistical Analysis Plans

3.6.1 Primary Endpoints

The following are the primary endpoints of the study:

• Frequency and grade of each solicited local and systemic reactogenicity AE during a 7-day follow-up period after each vaccination

- Frequency and grade of any unsolicited AEs during the 28-day follow-up period after each vaccination
- Frequency of any MAAE, SAE, and AESI from Day 1 to the EOS Visit at Month 13

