6.1.3 Solicited Safety Set (Solicited Local and Systemic Adverse Reactions)

A Solicited Safety Set is defined for each vaccination. The First (Second) Vaccination Solicited Safety Set consists of all participants in the Safety Set who have received the first

Protocol mRNA-1893-P101

(second) study vaccination and have contributed any solicited AR data (local or systemic reactogenicity events) from the time of first (second) study vaccination through the following 7 days (Day 1 through Day 8 for first vaccination and Day 29 through Day 36 for second vaccination).

The Solicited Safety Sets will be used for the analyses of solicited AEs.

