The percentage of participants who report each individual solicited local AR and solicited systemic AR from the time of study vaccination through the following 6 days (Day 1 through Day 7 and Day 29 though Day 35) will be tabulated by grade (including grades 1, 2, 3, and any grade >0), treatment group as defined in Section 7.1, and vaccination (first or second). These summaries will also be presented separately for flavivirus seropositive and seronegative participants.

Date Issued: 25May2021

Duration (in days) of each solicited AR will be summarized by treatment group and vaccination.

All solicited ARs, local solicited ARs, systemic solicited ARs, solicited ARs that are still on-going 6 days after vaccination, and solicited rash events will be presented in separate data listings.

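### Pause rules 4 and 5 label their window Days 1-8, which in the trial's study-day numbering is the first vaccination only; the label conflicts with the protocol's own definition and should be replaced by wording that covers either vaccination

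*Protocol*

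**What the plan says.** Rules 4 (local) and 5 (general) in Table 3 of Protocol 3.4.2.2 cover Grade 3 solicited events that last more than 24 hours. Both use the same window: "within the 7-day (Days 1-8) post-vaccination period". The threshold is at least 20% and at least 2 participants in the group. Footnote a adds that for the first 5 participants in a cohort "the pause rule will be considered met if 2 of the first 5 participants experience the same event regardless of dosing group". Footnote b sets the denominator: "The rate of adverse events and laboratory abnormalities will be computed based on the number of exposed participants who have provided safety data". None of this names the first or the second vaccination.

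Elsewhere, day labels count from the first dose. Dose 2 is on Day 29 and its diary visit is on Day 36. Its safety calls are on "Day 30 and Day 31 after the second vaccination" (Protocol 3.5.1). SAP 6.1.3 gives the two solicited windows as "Day 1 through Day 8 for first vaccination and Day 29 through Day 36 for second vaccination". SAP 7.6.1 also lists a range for each dose, "Day 1 through Day 7 and Day 29 though Day 35". The primary endpoint counts the same kind of event after both doses: "Frequency and grade of each solicited local and systemic reactogenicity AE during a 7-day follow-up period after each vaccination" (Protocol 3.6.1).

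**The concern.** Where the documents mean both doses, they list both day ranges or refer to each vaccination. Table 3 lists only the range that belongs to dose 1. SAP 5.4 has the unblinded statistician evaluate the pause criteria as Table 3 summarises them, so the label could be programmed as it stands.

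Rule 6 would not fully make up for this. It covers unsolicited events and laboratory abnormalities, and a solicited-type event counts as unsolicited only if "its onset occurs outside of the protocol-defined post-vaccination period for reporting solicited AEs". A diary-recorded reaction that starts within 7 days of dose 2 is therefore solicited and belongs under rules 4 and 5.

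Second doses are half of the planned vaccine injections: 24 of 48 per cohort. Protocol 3.4.2.1 bases escalation on data through 7 days after the first vaccination plus any cumulative data, so much of a cohort's dose-2 experience may arrive after the next dose level has opened. A proportion-based rule that missed dose 2 would be weakest at that point in this first-in-human trial.

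**Working it through.** **The texts side by side**

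| Source | What it implies for rules 4-5 |
|---|---|
| Table 3, rules 4-5: Days 1-8 | Dose 1 only, if these are study days |
| SAP 6.1.3: Days 1-8 first, Days 29-36 second | Days 1-8 means dose 1 |
| Protocol 3.5.1: dose-2 calls on Days 30 and 31 | Days are numbered from dose 1 |
| Glossary and Protocol 3.5.7.1.1: solicited period follows each vaccination | Both doses |
| Protocol 3.4.2.2: rules monitored in all study phases | Both doses |
| SAP 7.1: also defines a day count from the most recent vaccination, not tied to the pause rules | Days 1-8 could fit either dose |

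No sentence says that rules 4 and 5 apply after dose 2, and none says that they do not. The label and the definition conflict.

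**Size**

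The plan gives no operating characteristics for the pause rules. Its only probabilities, in Protocol 3.6.4, reproduce: 1 − 0.90^24 = 0.920 and 1 − 0.95^24 = 0.708.

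*Inputs from the documents:* 24 vaccine recipients per cohort, 4 of them among the first 5 participants; a threshold of at least 20% and at least 2; footnote a.

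*Assumptions:* the true rate p of a qualifying dose-2 reaction; no dose-1 reactors; no placebo reactors; all 24 in the denominator; any two reactors among the first 4 vaccinees count as having the same event.

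Threshold: 0.20 × 24 = 4.8, so 5 participants (4/24 = 16.7%; 5/24 = 20.8%).

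Study-day reading: no dose-2 reaction falls in Days 1-8, so dose-2 reactions fire rules 4-5 with probability 0 at any p.

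Both-doses reading, cumulative count, per rule per cohort:

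P(fire) = P(≥2 of 4) + P(0 of 4) × P(≥5 of 20) + P(1 of 4) × P(≥4 of 20)

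- p = 5%: 0.0140 + 0.8145 × 0.0026 + 0.1715 × 0.0159 = 0.0140 + 0.0021 + 0.0027 = 0.0188
- p = 10%: 0.0523 + 0.6561 × 0.0432 + 0.2916 × 0.1330 = 0.0523 + 0.0283 + 0.0388 = 0.1194

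| True dose-2 rate (assumed) | Study-day reading | Both doses |
|---|---|---|
| 5% | 0 | 1.9% |
| 10% | 0 | 11.9% |
| 20% | 0 | 57.4% |
| 30% | 0 | 89.9% |
| 40% | 0 | 98.8% |
| 50% | 0 | 99.9% |

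For rules 4 and 5 together, if independent: 1 − (1 − 0.0188)² = 3.7% at 5%, and 1 − (1 − 0.1194)² = 22.5% at 10%.

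The small-rate figures lean on footnote a. Without it, P(≥5 of 24) is 0.6% at 5% and 8.5% at 10%.

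**The case against.** The strongest reply is that the documents already settle the meaning. Rules 4 and 5 refer to a post-vaccination period, which for solicited events is defined as following each dose, and the rules are monitored in all phases. Protocol 3.4.5 has the unblinded statistician assess the Table 3 criteria in an analysis after each dosing cohort is complete, when dose-2 data exist. Days 29-36 would also be the wrong label for anyone given dose 2 late, so Days 1-8 may simply mean days counted from whichever dose was given.

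Most of this stands, and it makes both doses the likelier intention. It does not remove the conflict. The only explicit mapping of Days 1-8 to a vaccination assigns it to the first, and the dose-relative count in SAP 7.1 is not linked to the pause rules.

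A reader might go further and infer that dose 2 has no proportion-based monitoring at all. The documents do not support that. Rule 6 is proportion-based and has no day window, and Protocol 3.5.2 makes a solicited reaction reported verbally at a visit an unsolicited event, which rule 6 can count. Rules 1-3 carry no dose restriction. The investigator, medical monitor, Sponsor medical lead, IST or SMC may request a pause at any time. The calls 24 and 48 hours after dose 2 and the 24-hour contact rule for Grade 3 reactions also apply. Nor is there evidence that the rules were applied to dose 1 only. The IST and SMC charters, which may hold the operational detail, were not available.

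**Conclusion.** The point holds as an internal conflict in a safety trigger, not as a demonstrated gap in coverage. The label in rules 4 and 5 points to dose 1; the definition of the solicited period points to both doses, which is probably what was meant. If the label were followed, diary-recorded Grade 3 solicited reactions after dose 2 could not fire these two rules. A true dose-2 rate of 30% would then go uncounted by rules that would otherwise fire in about 90% of cohorts. That contrast depends on the literal reading, on assumed rates, and on there being no dose-1 reactors. It is worth correcting because the change is so small. Confidence is medium because the charters were not seen.

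**What to change.** In rules 4 and 5, replace the Days 1-8 phrase with: from the day of either vaccination through 7 days after it. The window should be relative to the actual date of each dose, because dose 2 may be given up to 14 days after Day 29 and fixed study days would miss late recipients. Footnote a and rule 6 can stay as they are.

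Optionally, add a sentence to footnote b saying that for rules 4 and 5 a participant with a qualifying event after either vaccination is counted once, over all exposed participants with at least one post-dosing visit. This only writes down what the reference to aggregate incidences above Table 3 already implies.

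The cost is wording in two table cells, with no new data. If both doses were always intended and counted cumulatively, the chance of a pause is unchanged. If the label was being applied literally, the added chance is the 1.9% (true rate 5%) or 11.9% (true rate 10%) per rule per cohort derived above. Each pause suspends dosing and requires notice to the Center for Biologics Evaluation and Research within 48 hours.

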3.4.2.3 Contraindications to Subsequent Vaccination

Prior to receiving a second vaccination, participants will be reassessed to ensure that they continue to meet eligibility requirements as outlined below.

The following events constitute absolute contraindications to any further administration of study vaccines. If any of these events occur during the study, the participant must not receive additional doses of vaccine but will be encouraged to continue study participation for safety through 12 months following last vaccination (Section 3.3.2).

- Anaphylaxis or systemic hypersensitivity reaction following the administration of vaccine
- Any SAE judged to be related to study vaccine
- Any AESI related to study vaccine (Appendix 2)
- Pregnancy
- Any CS medical condition that, in the opinion of the Investigator, poses an additional risk to the participant if he/she continues to participate in the study

The following events constitute contraindications to administration of study vaccine at certain points in time, and if any of these events occur at the time scheduled for vaccination, the participant may be vaccinated at a later date, within the time window specified in the Schedule of Events (Table 5), or the participant may be withdrawn from dosing at the discretion of the Investigator (Section 3.3):

- Acute moderate or severe infection with or without fever at the time of vaccination
- Fever, defined as body temperature $\geq 38.0^{\circ}\text{C}$ (100.4°F) at the time of vaccination

Participants with a minor illness without fever, as assessed by the investigator, can be administered study vaccines. Participants with a fever of 38.0°C (100.4°F) or higher will be recontacted within the time window acceptable for participation and reevaluated for eligibility.

3.4.3 Identity of Investigational Product

mRNA-1893 is a novel LNP-encapsulated mRNA-based vaccine directed against the prME structural protein of ZIKV. mRNA-1893 consists of CX-005809, an mRNA Drug Substance that is formulated into LNPs composed of 4 lipids: SM-102; cholesterol; DSPC; and PEG2000-DMG. mRNA-1893 is provided as a sterile liquid for injection at a concentration of 0.5 mg/mL in 100 mM Tris buffer, 7% propylene glycol, and 1 mM DTPA.

The placebo is 0.9% sodium chloride injection, United States Pharmacopeia (USP) or British Pharmacopeia (BP).

3.4.4 Management of Clinical Supplies

3.4.4.1 Study Vaccine Packaging and Storage

The Sponsor will provide the investigator and study site with adequate quantities of mRNA-1893. The placebo (0.9% sodium chloride injection, USP or BP) is commercially available and will be supplied by the Sponsor or CRO. mRNA-1893 will have all required labeling per regulations. mRNA-1893 will be supplied to the pharmacy in an unblinded manner. Each vial will be individually labeled for future participant identification purposes.

mRNA-1893 will be supplied as a sterile liquid for injection at a concentration of 0.5 mg/mL. The sterile product will be provided in 2-mL glass vials with a 0.85-mL fill volume. The unblinded study site pharmacy personnel will prepare a single dose (0.5 mL) for each participant based on the cohort and randomization assignment. A pharmacy manual will be available, and training provided.

mRNA-1893 vaccine must be stored in a secure area with limited access (unblinded pharmacy staff only), protected from moisture and light, and be stored at $-20^{\circ}\text{C} \pm 5^{\circ}\text{C}$. The freezer should have an automated temperature recording and alert system. There must be an available back-up freezer. The freezers must be connected to a back-up generator. The

pharmacy must have in place a 24-hour alert system that allows for rapid response in case of freezer malfunctioning. In addition, vaccine accountability study staff (e.g., the unblinded pharmacy personnel) are required to keep a temperature log to establish a record of compliance with these storage conditions. The placebo will be stored according to the instructions on the product label and must also comply with storage in a restricted access area. Only vaccine accountability study staff (e.g., unblinded pharmacy personnel) should have access to the products used in this study.

The site is responsible for reporting any mRNA-1893 vaccine that was not temperature controlled during shipment or during storage to the unblinded site (pharmacy) monitor. Such mRNA-1893 will be retained for inspection by the unblinded monitor and disposed of according to approved methods.

3.4.4.2 Study Vaccine Accountability

It is the investigator's responsibility that the unblinded pharmacy personnel maintain accurate records of receipt of all mRNA-1893 vaccine, including dates of receipt. In addition, accurate records will be kept regarding when and how much mRNA-1893 is dispensed and used by each participant in the study. Reasons for departure from the expected dispensing regimen must also be recorded. To satisfy regulatory requirements regarding vaccine accountability, all mRNA-1893 vaccine will be reconciled and retained until study conclusion. At that time, mRNA-1893 vaccine will be destroyed or returned to the Sponsor according to applicable regulations.

3.4.5 Blinding

This is an observer-blind study. The Sponsor, investigator, study participants, site monitors, and study staff will be blinded to the study vaccine administered until trial end, with the following exceptions:

Unblinded pharmacy personnel (of limited number) will be assigned to vaccine
accountability procedures and will prepare and administer mRNA-1893 (or placebo)
to all participants. The designee(s) will have no study functions other than study
vaccine management, documentation, accountability, preparation, and administration.
They will not be involved in participant evaluations and will not reveal the study

vaccine identity to either the participant or the study site personnel involved in the conduct of the study unless this information is necessary in the case of an emergency.

- An unblinded study monitor, not involved in other aspects of monitoring, will be assigned as the vaccine accountability monitor. They will have responsibilities to ensure that the site is following all proper vaccine accountability, preparation, and administration procedures.
- An unblinded statistician will provide a descriptive analysis of safety and immunological endpoints after the completion of each dosing cohort, including evaluation of the pause rules criteria summarized in Table 3 (Section 3.4.2.2). The interim analyses of immunogenicity data will be performed as outlined in Section 3.6.8.
- The Sponsor will remain blinded to individual treatment assignment throughout the Vaccination Phase through Visit 9 (28 days post last vaccination) for each vaccine cohort/dose level of the study. Once the Vaccination Phase for each vaccine cohort/dose level is completed, at the time of the Day 57 Interim Analysis pre-identified Sponsor team members will be unblinded to review treatment level results and individual listings and will remain unblinded. Study sites will remain blinded to individual treatment assignments until trial end.

The dosing assignment will be concealed by having the unblinded designee(s) (e.g., unblinded pharmacy personnel) prepare the study vaccine in a secure location that is not accessible to other study staff. The syringe used for administration will maintain the blind at the time of vaccination (i.e., a sleeve will be used, as the vaccine substance will be distinguishable in appearance between the mRNA-1893 and placebo). Only pharmacy staff will conduct the vaccination procedure. Once the vaccination is completed, the blinded study staff will perform further assessments and interact with the participants. Access to the randomization code will be strictly controlled at the pharmacy.

